## 16. APPENDICES

### 16.1. Appendix 1: Protocol Deviation Management and Definitions for Per Protocol Population

Subjects with important protocol deviations considered to potentially have an effect on the primary efficacy analysis will be excluded from the Per Protocol (PP) population. The decision to exclude a subject from the PP population or exclude part of their data from the PP population will be made prior to breaking the blind.

#### 16.1.1. Exclusions from Per Protocol Population

A subject meeting any of the following criteria will be excluded from the Per Protocol population:

Number	Exclusion Description
01	Inclusion #3 – Insufficient evidence that subject has been diagnosed with HES for at least 6 months at randomization (Visit 2).
02	Inclusion #4 – Subject did not have a history of two or more flares within the past 12 months prior to screening (Visit 1), with at least one HES flare not related to a decrease in HES therapy during the 4 weeks prior to the flare.
03	Inclusion #5 – Subject did not have a blood eosinophil count $\geq 1000$ cells/ $\mu\text{L}$ collected during screening (within 4 weeks prior to randomization). Investigators were permitted to use local laboratory results to meet this inclusion criteria, therefore if the screening central laboratory blood eosinophil count is $< 1000$ cells/ $\mu\text{L}$ but a local laboratory blood eosinophil count $\geq 1000$ cells/ $\mu\text{L}$ is available during screening the subject will not be considered a protocol deviation or excluded from the Per Protocol population.
04	Inclusion #6 – Subject was not on a stable dose of HES therapy for the 4 weeks prior to randomization (Visit 2).
05	Incorrect study treatment administered at any point during the study i.e. subject received placebo instead of mepolizumab or vice versa.
06	Subject received a medication or herbal remedy which may alter the course of HES or interact with the study treatment with the exception of HES therapy to treat a HES flare.

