6.10. Concomitant Medications and Non-Drug Therapies

6.10.1. Permitted Medications and Non-Drug Therapies

Use of standard HES therapy including OCS, immunosuppressive or cytotoxic therapy (e.g., hydroxyurea, IFN α , cyclosporine, imatinib, methotrexate, azathioprine) will be permitted during the study. As specified in Inclusion Criterion #6, subjects must be on a stable dose of HES therapy for the 4 weeks prior to randomization (Visit 2) [Section 5.1]. The same regimen of HES therapy must be maintained throughout the 32-week study treatment period unless there is worsening of symptom(s) that requires an increase in therapy. If a subject has worsening of symptom(s) and requires an increase in therapy after randomization, the subject will be considered to be experiencing a flare (Section 7.3.1). Once the subject regains disease control, the investigator is encouraged, as medically appropriate, to adjust the dose of HES therapy back to the level prior to the disease worsening.

A reduction in standard HES therapy dose for safety reasons, with return to the original dosing regimen when possible, is permitted in consultation with the GSK Medical Monitor.

Additional therapies required to treat non-HES related medical conditions during the study are permitted in consultation with the GSK Medical Monitor and must be prospectively captured in the CRF.

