6.10.2. Prohibited Medications and Non-Drug Therapies

Initiation of new medications or herbal remedies which may alter the course of HES or interact with the study treatment is prohibited within their specified timeframe and throughout the study (Visit 0 to Visit 11 inclusive) with the exception of HES therapy to treat an HES flare (Section 7.3.1).

In addition, the following medications will be prohibited:

- Any investigational agents (biologic or non-biologic) within the 30 days or 5 drug half-lives whichever is longer, prior to screening (Visit 1), and until Visit 11. The term “investigational” applies to any drug not approved for sale in the country in which it is being used or investigational formulations of marketed products.
- Any other biologic agents (except for IFN α): within 30 days or 5 half-lives, whichever is longer, of screening (Visit 1), and until Visit 11.

In the event that the use of a prohibited medication is identified by the study site, the investigator must use clinical judgment in balancing protocol compliance (discontinuing the medication) and subject safety. The investigator should assess whether the medication is required or likely to be required to maintain subject’s health in control. The investigator also should assess whether the medication can be stopped after subject’s health is re-established.

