9.2. Sample Size Considerations

9.2.1. Sample Size Assumptions

This study is designed to test the superiority of mepolizumab versus placebo.

The primary efficacy endpoint is the proportion of subjects who experience an HES flare during the 32-week study treatment period. The power calculation assumes that 60% of subjects on placebo will experience an HES flare during the 32-week study treatment period. With a two-sided 5% level of significance and a sample size of 40 randomized subjects per arm, the null hypothesis will be rejected if the observed proportion of patients with an HES flare on placebo is 60% and on mepolizumab is 35% or less. If the true population proportion of subjects who would experience an HES flare during the 32-week study treatment period on placebo is 60% and on mepolizumab is 22%, the study has 90% power for demonstrating a statistically significant result for this assumed true population effect.

This endpoint is novel, and has not explicitly been used in clinical trials of HES. There is therefore little previous data on which to base estimates of the number of subjects who will experience an HES flare during the 32-week study treatment period.

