16.10.5. Efficacy Tables

Efficacy: Tables					
No.	Population	IDSL / Example Shell	Title	Programming Notes	Deliverable
HES Flare					
2.1.	ITT	EFF_T1	Overview of HES Flares		SAC
2.2.	ITT	EFF_T2	Summary of Frequency of All HES Flares		SAC
2.3.	ITT	EFF_T3	Primary Analysis of Proportion of Subjects Who Experience a HES Flare During the 32-Week Treatment Period (Treatment Policy Estimand)		Headline
2.4.	ITT	EFF_T3a	Supportive Analysis of Proportion of Subjects Who Experience a HES Flare During the 32-Week Treatment Period (While on Treatment Estimand)		Headline
2.5.	PP	EFF_T3	Supportive Analysis of Proportion of Subjects Who Experience a HES Flare During the 32-Week Treatment Period (Treatment Policy Estimand, PP Population)		Headline
2.6.	ITT	EFF_T3b	Sensitivity Analysis of Proportion of Subjects Who Experience a HES Flare During the 32-Week Treatment Period (Treatment Policy Estimand, Alternative Missing Data Imputation Strategy #1)		Headline
2.7.	ITT	EFF_T3c	Sensitivity Analysis of Proportion of Subjects Who Experience a HES Flare During the 32-Week Treatment Period (Treatment Policy Estimand, Alternative Missing Data Imputation Strategy #2)		Headline
2.8.	ITT	EFF_T3	Sensitivity Analysis of Proportion of Subjects Who Experience a HES Flare During the 32-Week Treatment Period (Treatment Policy Estimand, Excluding Subjects From Site PPD )		SAC

Efficacy: Tables					
No.	Population	IDSL / Example Shell	Title	Programming Notes	Deliverable
2.9.	ITT	EFF_T3	Analysis of Proportion of Subjects Who Experience a HES Flare During the 32-Week Treatment Period by Age (Treatment Policy Estimand)	Descriptive summary only; do not present p-values.	SAC
2.10.	ITT	EFF_T3	Analysis of Proportion of Subjects Who Experience a HES Flare During the 32-Week Treatment Period by Sex (Treatment Policy Estimand)	Descriptive summary only; do not present p-values.	SAC
2.11.	ITT	EFF_T3	Analysis of Proportion of Subjects Who Experience a HES Flare During the 32-Week Treatment Period by Race (Treatment Policy Estimand)	Descriptive summary only; do not present p-values.	SAC
2.12.	ITT	EFF_T3	Analysis of Proportion of Subjects Who Experience a HES Flare During the 32-Week Treatment Period by Region (Treatment Policy Estimand)	Descriptive summary only; do not present p-values.	SAC

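### Under the SAP's definition of a flare, per-protocol criterion 06 makes exclusion for newly started rescue therapy depend on whether that therapy counted as an endpoint event

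*SAP*

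**What the plan says.** SAP 16.1.1 lists six grounds for exclusion from the PP population and applies them without discretion. The sixth covers a subject who took any product "which may alter the course of HES or interact with the study treatment with the exception of HES therapy to treat a HES flare". SAP 7.1.1 and 16.6.4 give HES flare one meaning, the endpoint event: a documented HES manifestation needing an OCS increase of at least 10 mg/day for 5 days or any cytotoxic or immunosuppressive increase or addition, or two or more courses of blinded active OCS.

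The criterion descends from Protocol 6.10.2. That section prohibits starting new medications that may alter HES, "with the exception of HES therapy to treat an HES flare (Section 7.3.1", and so points to the same endpoint definition. Protocol 6.10.1 requires a constant HES regimen "unless there is worsening of symptom(s) that requires an increase in therapy". It then calls any such symptomatic increase a flare, again citing 7.3.1 but naming no dose or duration. Protocol 4.4 does the same.

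SAP 16.1 describes PP exclusions as important protocol deviations, decided before the blind is broken. The PP repeat of the primary analysis is Table 2.5, "Supportive Analysis of Proportion of Subjects Who Experience a HES Flare During the 32-Week Treatment Period (Treatment Policy Estimand, PP Population". It is a Headline deliverable, and its odds ratio also appears in Headline Figure 2.2 next to the primary one. SAP Section 4 labels the PP analysis supplementary.

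**The concern.** A PP exclusion should describe departure from protocol and be decidable without knowing whether the subject had the outcome. Take two subjects who both worsen and are both started on HES therapy. If the therapy meets 7.3.1, the first is scored as an event and kept. If it falls short, the second is scored as a non-event and, on the SAP's definition, is not covered by the exemption and is excluded. The act is of the same kind; only the outcome classification differs.

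Deciding exclusions before unblinding does not help here. It hides the arm, but flares under definition (a) sit on the eCRF flare page and are visible to whoever applies the rule.

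At stake is a supportive odds ratio that will be read beside the primary result as if it were corroboration.

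**Working it through.** **1. Which rescue does criterion 06 reach?** Taking flare as SAP 7.1.1 defines it:

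| HES therapy given for worsening | Endpoint event? | Criterion 06 |
|---|---|---|
| Any cytotoxic/immunosuppressive start or increase | Yes | Kept |
| OCS newly started, at or above the 7.3.1 threshold | Yes | Kept |
| OCS newly started, lower or shorter (subject with 0 mg at baseline, foreseen in SAP 5.4.1.1) | No | Excluded |
| Budesonide or fluticasone newly started (SAP 5.4.1.1 classes these as other HES therapy, not OCS) | No | Excluded |
| Sub-threshold increase of existing OCS | No | Probably not reached: allowed by 6.10.1, and not an initiation under 6.10.2 |
| A single course of blinded active OCS | No (a flare only at the second course) | Not exempt as worded, but directed by Protocol 6.4, so presumably not a deviation |

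The outcome-dependent rows are the third and fourth.

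**2. The plan's own figure.** Inputs from Protocol 9.2.1: "With a two-sided 5% level of significance and a sample size of 40 randomized subjects per arm"; "The power calculation assumes that 60% of subjects on placebo will experience an HES flare"; 22% on mepolizumab; "the study has 90% power for demonstrating a statistically significant result". Continuity-corrected normal approximation:

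power = Φ{[|p1 − p2| − 1/n − 1.96·√(2p̄(1 − p̄)/n)] / √([p1(1 − p1) + p2(1 − p2)]/n)}

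With p1 = 0.60, p2 = 0.22, p̄ = 0.41, n = 40: (0.355 − 0.2156)/0.1014 = 1.37, power 91.5%. Exact enumeration with Fisher's test gives 91.9%. The uncorrected approximation gives 94.8%. The stated significance boundary (60% v 35%) also reproduces: 24/40 v 14/40, Fisher p = 0.043; 24/40 v 15/40, p = 0.073. The planning rates are therefore a sound base, taken as 24/40 v 9/40.

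**3. Effect of removing non-events.** Removing a fraction f of an arm's non-flare subjects multiplies that arm's flare odds by 1/(1 − f). Hence

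OR(PP) = OR(ITT) × (1 − f_placebo)/(1 − f_mepolizumab).

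Each arm's flare proportion can only rise. The odds ratio moves towards mepolizumab only if f_placebo exceeds f_mepolizumab; equal fractions leave it unchanged.

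**4. Numbers.** Non-flare subjects at base: 16 placebo, 31 mepolizumab. Base OR = (9/31)/(24/16) = 0.194. The removed counts are **assumptions**; the documents give none.

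| Non-flare removed (placebo, mepolizumab) | Flare proportions | Difference (points) | OR |
|---|---|---|---|
| 0, 0 | 60.0% v 22.5% | 37.5 | 0.194 |
| 6, 0 | 70.6% v 22.5% | 48.1 | 0.121 |
| 4, 1 | 66.7% v 23.1% | 43.6 | (9/30)/(24/12) = 0.150 |
| 4, 4 | 66.7% v 25.0% | 41.7 | 0.167 |
| 2, 4 (12.5%, 12.9%) | 63.2% v 25.0% | 38.2 | 0.194 |
| 4, 8 (25.0%, 25.8%) | 66.7% v 28.1% | 38.5 | 0.196 |
| 0, 4 | 60.0% v 25.0% | 35.0 | (9/27)/(24/16) = 0.222 |

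If instead 4 placebo and 1 mepolizumab subjects *with* a flare are excluded for some other non-exempt product, the result is 20/36 v 8/39 (55.6% v 20.5%), OR 0.206. The placebo rate falls and the effect shrinks.

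**5. A borderline case.** Start from 24/40 v 15/40, Fisher p = 0.073. Removing 2 placebo non-flare subjects gives p = 0.041; removing 4 from each arm gives p = 0.058. Fisher's test stands in here for the stratified CMH test, since stratum counts are not given.

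**The case against.** The strongest reply is that the protocol itself treats any symptomatic increase in therapy as a flare (4.4 and 6.10.1, both citing 7.3.1), so rescue of any size would be exempt. Further, 6.10.2 concerns starting new medication, a permitted increase is not a deviation, and SAP 16.1 confines PP exclusion to important deviations. Criterion 06 cannot sensibly be read apart from 6.10.2, because taken literally it would remove everyone on background HES therapy.

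Much of this stands. It takes increases of existing therapy, and probably blinded OCS, out of reach and leaves a small affected set. It does not settle the newly started sub-threshold case. The section that 4.4 and 6.10.1 cite contains a threshold, the SAP's own definition is the endpoint event, and SAP 16.1.1 says that subjects meeting a criterion will be excluded. The documents conflict and the SAP does not resolve it.

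Two further replies also stand. A reader might infer that only flare-free subjects can be removed. The documents do not support that: exclusion is per subject, so someone with an endpoint flare who also took another non-exempt product is removed, as is someone who took one and then withdrew without a flare, whom SAP 7.1.3.1 scores as a failure. A reader might also infer that the treatment effect will be inflated. That needs arm-specific exclusion fractions that appear nowhere in the documents. More sub-threshold rescue on placebo is plausible if the drug works, but the shift could be nil or reversed.

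Exclusions are summarised (Table 1.8) and listed (Listing 8), which helps, but no split by flare status is specified.

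**Conclusion.** The point holds in a limited form. On the SAP's definition of a flare, criterion 06 is an outcome-dependent exclusion rule for HES therapy newly started for worsening, and it feeds a Headline table and figure. Its effect on the PP odds ratio has no determined direction: over the assumed counts of non-flare subjects removed, it runs from 0.121 to 0.222 against 0.194. It favours mepolizumab only where a larger fraction of non-flare subjects is removed on placebo.

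It would be wrong to read this as a threat to the primary result. The ITT analysis uses a treatment-policy strategy for alternative HES medications and keeps these subjects, and the PP analysis is outside the testing hierarchy. The change is still worth making: it is cheap, and without it the supportive result cannot be taken at face value.

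The conclusion rests on reading the exemption through SAP 7.1.1, and on at least some sub-threshold rescue being newly started rather than an increase of existing therapy.

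**What to change.** Before unblinding, amend SAP Appendix 1 so that PP exclusion does not depend on flare status:

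- State that HES therapy given after first dose for HES worsening, whether or not it meets 7.3.1, is not a PP exclusion, and that blinded OCS is not one either.
- Limit criterion 06 to other prohibited products.
- Reconcile the use of the word flare in criterion 06 with Protocol 4.4, 6.10.1 and 6.10.2. This concerns the analysis set only and changes nothing in how subjects are managed.
- Report criterion-06 exclusions by arm and flare status.

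The cost is a few lines of text and one extra breakdown in an existing display. The downside is a slightly larger, less restrictive PP set that retains some subjects with sub-threshold rescue.

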**16.2. Appendix 2: Schedule of Activities**

**16.2.1. Protocol Defined Schedule of Events**

Procedures	Pre-screen	Screen	Randomi- zation	Double-blinded treatment period												Additional follow-up	
				3	4	5	6	7	8	9	10	11 End-of- treatment	Flare 	3-11 for subjects who prematurely discontinue study treatment 	EW		12
Study visit	0	1	2														
Study week		Up to ~4 weeks (wks)	0	2 ±5 days	4 ±1 wks	8 ±1 wks	12 ±1 wks	16 ±1 wks	20 ±1 wks	24 ±1 wks	28 ±1 wks	32 ±1 wks					~12 wks after last dose ±1 wks
Informed consent 	X																
Demography	X																
Medical history		X															
History of HES (diagnosis/flare) and treatment (past 12 months)	X																
CV history/risk factors		X															
Inclusion/exclusion		X	X														
Parasite screening 		X															
Efficacy and PRO assessments																	
Subject-RTS 					X	X	X	X	X	X	X	X	X				X
SSR 			X		X	X	X	X	X	X	X	X	X				
Modified MSAS-SF 			X		X	X		X		X		X	X			X	
PROMIS sleep and physical function scales 			X		X	X		X		X		X					
SF-36 v2 			X		X	X	X	X	X	X	X	X	X	X		X	
WPAI-GH v2 			X		X	X	X	X	X	X	X	X	X			X	
Steroid perception questionnaire 			X														
HES Core Assessments (clinician)			X		X	X	X	X	X	X	X	X	X	X	X	X	

CONFIDENTIAL

200622

Procedures	Pre-screen	Screen	Randomi- zation	Double-blinded treatment period											Additional follow-up	
assessment) /Flare detail																
Clinician-RTS					X	X	X	X	X	X	X	X				X

Procedures	Pre- screen	Screen	Randomi- zation	Double-blinded treatment period												Additional follow-up
				3	4	5	6	7	8	9	10	11 End-of- treatment	Flare 	3-11 for subjects who prematurely discontinue study treatment 	EW	
Study visit	0	1	2	3	4	5	6	7	8	9	10	11 End-of- treatment	Flare 	3-11 for subjects who prematurely discontinue study treatment 	EW	12
Study week		Up to ~4 weeks (wks)	0	2 (± 5 days)	4 ±1 wks	8 ±1 wks	12 ±1 wks	16 ±1 wks	20 ±1 wks	24 ±1 wks	28 ±1 wks	32 ±1 wks				~12 wks after last dose ±1 wks
HCRU			X		X	X	X	X	X	X	X	X			X	
Spirometry			X			X		X		X		X	X			
Echocardiogram 		X										X	X			
Safety assessments																
Physical examination 		X	X		X	X	X	X	X	X	X	X	X			
Height and weight 		X	X					X				X			X	
Concomitant meds including maintenance OCS	X	X	X	X	X	X	X	X	X	X	X	X	X	X	X	
Vital signs 		X	X		X	X	X	X	X	X	X	X	X		X	
ECG		X										X	X			
AEs			X	X	X	X	X	X	X	X	X	X	X	X	X	X
SAEs		X	X	X	X	X	X	X	X	X	X	X	X	X	X	X
Laboratory assessments																
Hematology 		X	X	X	X	X	X	X	X	X	X	X	X	X	X	X 

CONFIDENTIAL

200622

Procedures	Pre-screen	Screen	Randomization	Double-blinded treatment period												Additional follow-up
Chemistry 		X			X	X	X	X	X	X	X	X	X	X	X 	X 
Troponin		X			X	X	X	X	X	X	X	X	X	X	X 	X 
Pregnancy test 		X	X		X	X	X	X	X	X	X	X	X		X 	X 
Aldolase		X			X	X	X	X	X	X	X	X	X			
Lipoproteins (fasting) 		X														
Urinalysis 		X										X		X 	X 	
Hep B & C serology 		X														
F/P status 		X														
T-cell profile		X										X		X 	X 	
Total IgE			X													

Procedures	Pre-screen	Screen	Randomization	Double-blinded treatment period												Additional follow-up
				3	4	5	6	7	8	9	10	11 End-of-treatment	Flare 	3-11 for subjects who prematurely discontinue study treatment 	EW	
Study visit	0	1	2	3	4	5	6	7	8	9	10	11 End-of-treatment	Flare 	3-11 for subjects who prematurely discontinue study treatment 	EW	12
Study week		Up to ~4 weeks (wks)	0	2 (± 5 days)	4 ±1 wks	8 ±1 wks	12 ±1 wks	16 ±1 wks	20 ±1 wks	24 ±1 wks	28 ±1 wks	32 ±1 wks				~12 wks after last dose ±1 wks
PK					X			X				X		X 	X 	X 
PD (IL-5)			X									X	X			
Immunogenicity (Anti-drug antibody)			X					X				X		X 	X 	X 
Genetics 			X													
Sample collection for biomarker sub-study 			X									X	X	X 	X 	
Investigational product & other study treatment																

**CONFIDENTIAL**

200622

Procedures	Pre-screen	Screen	Randomization	Double-blinded treatment period												Additional follow-up
Study treatment administration 			X		X	X	X	X	X	X	X					
Dispense/collect blinded OCS			X	X	X	X	X	X	X	X	X	X		X	X	
Interactive Response Technology (IRT)/electronic CRF (eCRF)/electronic Diary (eDiary)																
Register visit on IRT	X	X	X	X	X	X	X	X	X	X	X	X	X	X	X	X
Complete eCRF		X	X	X	X	X	X	X	X	X	X	X	X	X	X	X
Dispense (D) /collect (C) eDiary 		D										C		C for Visit 11	C	
Review eDiary			X	X	X	X	X	X	X	X	X	X		X	X	

EW: Early withdrawal

1. Pre-screen visit to obtain informed consent can occur on the same day as Visit 1, but informed consent must be obtained prior to starting Visit 1 procedures.
2. Parasitic screening is only required in countries with high-risk or for subjects who have visited high-risk countries in the past 6 months. Sites should use local laboratories.
3. Subject-completed assessments are done at the beginning of a visit.
4. Echocardiogram is performed to support CV assessment at screening and at the end of study treatment for all subjects. Echocardiogram at Visit 1 is required unless there is a documented result within the previous 6 months from Visit 1.
5. Findings during physical examination related to HES will be recorded in the HES Core Assessments/flare detail.
6. Height to be measured at screening only.
7. Vital sign measurements will include temperature, systolic and diastolic blood pressure and pulse rate.
8. During the treatment period, all laboratory samples (Protocol Table 4) should be obtained pre-dose.
9. Refer to protocol Section 6.4 for additional blood draw between the scheduled clinical visits for subjects who will administer blinded OCS.
10. Clinical chemistry will include analytes and liver chemistry monitoring.
11. Negative urine pregnancy test result must be confirmed prior to dosing in women of reproductive potential.
12. Lipoprotein (fasting) included in clinical chemistry. Subject must be in a fasting state. If the subject has not fasted, he/she may return to the clinic to collect this sample.
13. Urine tests are done using dipstick. If found abnormal, the urine sample will be sent to the central laboratory for further testing.
14. If test was performed within 3 months prior to randomization, testing at screening is not required.
15. F/P test is required if no documented results are available.
16. Informed consent for optional sub-studies (e.g., genetics research) must be obtained before collecting a sample. Genetic sample collection is recommended at Visit 2, but may be drawn at any time after the subject is consented and randomised.
17. Sample collection for the optional biomarker sub-study should be done after obtaining a written consent.
18. The date and time of the administration of study treatment will be recorded in the CRF. For safety monitoring requirement, refer to protocol Section 6.2.
19. Assessments will be collected when possible depending on the clinical status during worsening of symptoms between scheduled clinic visits to evaluate for a HES flare. Spirometry for a respiratory flare, and troponin, echocardiogram, & ECG for a CV flare will be performed (Selective assessments depending on the type of flare are noted in the table with the gray shade). Echocardiogram will be performed only if there is a change in HF classification (see protocol Section 12.7) and/or the investigator determines that there is a need for assessment. When attending the clinic visit at the time of a suspected HES flare is not possible, the investigator should make every effort to evaluate the subject via telephone and complete the HES Core Assessments (protocol Section 7.3.2).
20. Subjects who prematurely discontinue study treatment will continue to attend 4-weekly scheduled clinic visit and complete these assessments. Blood samples for hematology will be collected at these visits for blinded blood eosinophil monitoring (protocol Section 6.4). All other laboratory assessments are completed at 4 and 12 weeks after the last dose only as noted in footnote #21.
21. Approximately 4 weeks after the last dose of study treatment, every attempt should be made to collect urine and blood samples for laboratory assessments. In addition, all subjects will be brought in for an additional follow-up visit 12 weeks after the last dose, including the collection of a blood sample for measurement of anti-drug antibodies and PK, unless the subject receives open-label mepolizumab according to the protocol criteria at that time.
22. Subjects will complete BFI and HES daily symptoms (HES-DS) in the eDiary on a daily basis. Subjects must complete the eDiary for at least 7 days prior to randomization. Subjects who prematurely discontinue study treatment will continue daily eDiary completion and return the eDiary at Visit 11 for EW.

